	
Screening MRI scan may be used if no positive Gd-enhancing scan exist from prior year).
 
 • Neurologically stable within 1 month prior to randomization
Key Exclusion criteria	
 • Patients with primary progressive MS or SPMS without disease activity • Patients meeting criteria for neuromyelitis optica • Disease duration of more than 10 years in patients with an EDSS score of 2 or less • Pregnant or nursing (lactating) women • Women of child-bearing potential unless using highly effective methods of contraception during study drug dosing and for 12 months post-dosing • Sexually active males unless they agree to use condom during intercourse while on study drug • Patients with an active chronic disease of the immune system other than MS • Patients with neurological findings consistent with PML or confirmed PML • Patients at risk of developing or having reactivation of hepatitis: positive results at Screening for serology markers for hepatitis A, B, C and E (HA, HB, HC, and HE) indicating acute or chronic infection • Patients with active systemic infections or known to have AIDS or to test positive for HIV antibody at Screening • Patients at risk of developing or having reactivation of syphilis or tuberculosis • Have received any live or live-attenuated vaccines within 2 months prior to randomization • Have been treated with medications as specified or within timeframes specified (e.g. corticosteroids, ofatumumab, rituximab, ocrelizumab, alemtuzumab, natalizumab, cyclophosphamide, teriflunomide, leflunomide, etc.) • Any other disease or condition that could interfere with participation in the study according to the study protocol, or with the ability of the patients to cooperate and comply with the study procedures.
Study treatment	
Ofatumumab (OMB157G) 20 mg sc injections once every 4 (q4) weeks (following initial loading regimen of three 20 mg sc doses/week in first 14 days) + teriflunomide-matching placebo capsules orally once daily
 
Teriflunomide 14 mg capsules orally once daily + ofatumumab-matching sc placebo injections

Efficacy assessments	
MS relapse, Expanded Disability Status Scale (EDSS), Magnetic Resonance Imaging (MRI), Timed 25-Foot Walk (T25FW), Nine Hole Peg Test (9HPT), Symbol Digit Modalities Test (SDMT), Multiple Sclerosis Impact Scale (MSIS-29), Neurofilament light chain (NfL)

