Due to the long elimination of teriflunomide (8 months up to 2 years), all patients who have discontinued study drug and have completed at least 9 months of follow up (in the Treatment epoch or the Safety FU epoch) and who plan to become pregnant/father a child or do not agree to continue to use highly effective contraception, should undergo the teriflunomide-accelerated elimination procedure (AEP) described in Section 7.8. To protect study blind, the decision to do the accelerated elimination procedure must be made without knowledge of the core study treatment assignment. Patients may not re-start study drug after accelerated elimination.

Patients who complete the Treatment epoch (while on study drug) may be eligible to participate in the long-term, open-label ofatumumab **Extension study**. The details of the design and assessments of the Extension study will be described in a separate protocol. This extension will last for up to 5 years for individual patients or until the development of ofatumumab in relapsing MS has been decided to be discontinued, if earlier.

Figure 3-1 Study design

*Patients who complete the Treatment Epoch and do not enter the planned Extension study or who prematurely discontinue study drug and do not agree to complete the study Treatment epoch or have less than 9 months of follow up after study drug discontinuation, will enter the Safety FU epoch. **Extension study will be conducted under separate protocol. M=month, EOS=End of Study, FU=Follow-Up, po qd= orally once a day

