 - Use of oral (estrogen and progesterone), injected or implanted hormonal methods of contraception or placement of an intrauterine device or intrauterine system or other forms of hormonal contraception that have comparable efficacy (failure rate < 1%), for example hormone vaginal ring or transdermal hormone contraception. In case of use of oral contraception, women should have been stable on the same pill for a minimum of 3 months before taking study drug.

Note: Women are considered post-menopausal and not of child bearing potential if they have had 12 months of natural (spontaneous) amenorrhea with an appropriate clinical profile (e.g. age appropriate, history of vasomotor symptoms) or have had surgical bilateral oophorectomy (with or without hysterectomy), total hysterectomy or tubal ligation at least six weeks ago. In the case of oophorectomy alone, only when the reproductive status of the woman has been confirmed by follow up hormone level assessment is she considered not of child bearing potential.
7. Sexually active males, unless they agree to use a condom during active treatment. Male patients should not father a child in this period. Given the long elimination time of teriflunomide of up to 2 years, the male patient wishing to father a child during the study should discontinue study drug and undergo the accelerated elimination process (refer to

Section 7.8). A condom is required to be used also by vasectomized males in order to prevent accidental exposure of their female partner to study drug via seminal fluid

8. Patients with an active chronic disease (or stable but treated with immune therapy) of the immune system other than MS (e.g. rheumatoid arthritis, scleroderma, Sjögren's syndrome, Crohn's disease, ulcerative colitis, etc.) or with immunodeficiency syndrome (hereditary immune deficiency, drug-induced immune deficiency)
9. Patients with active systemic bacterial, viral or fungal infections, or known to have AIDS or to test positive for HIV antibody at Screening
10. Patients with neurological findings consistent with PML or confirmed PML

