7.8 Accelerated elimination procedure related to active comparator teriflunomide

Teriflunomide is eliminated slowly from the plasma. Without an accelerated elimination procedure, it takes on average 8 months to reach plasma concentrations less than 0.02 mg/L, although, because of individual variations in drug clearance, it may take as long as 2 years. The teriflunomide label includes guidance on accelerated elimination of teriflunomide in patients in whom a rapid elimination is desirable.

In order to protect the blind and integrity of the present study (double-blind/double-dummy study of ofatumumab vs teriflunomide), a decision to initiate the teriflunomide-specific accelerated elimination procedure must be taken without knowledge of the patient's treatment assignment.

It is recommended that patients who permanently discontinue study drug undergo the accelerated elimination procedure (during study Treatment epoch or during Safety Follow-up) if this is in the patient's best interest as determined by the Investigator or in order to facilitate further treatment or management decisions. This procedure (described below) must be carried out under the supervision of the Investigator.

For patients who develop an SAE (e.g. serious infection, liver event) leading to study drug discontinuation per protocol criteria or per the Investigators clinical judgment, an accelerated elimination may similarly be considered.

As described in the EU and US labels for teriflunomide (Aubagio[®]), elimination of teriflunomide can be accelerated by either of the following procedures:

- Administration of cholestyramine 8 g every 8 hours for 11 days. If cholestyramine 8 g 3 times a day is not well tolerated, cholestyramine 4 g 3 times a day can be used.
- Administration of 50 g oral activated charcoal powder every 12 hours for 11 days.
- If either elimination procedure is poorly tolerated, treatment days do not need to be consecutive unless there is a need to lower teriflunomide plasma concentration rapidly.

The procedure should be documented on the Accelerated Elimination Procedure CRF. Any AEs reported during the procedure must be recorded on the AE CRF.

8 Data review and database management

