10.2 Informed consent procedures

Eligible patients/subjects may only be included in the study after providing written (witnessed, where required by law or regulation), IRB/IEC-approved informed consent, or, if incapable of doing so, after such consent has been provided by a legally acceptable representative(s) of the patient. In cases where the patient's representative gives consent, the patient must be informed about the study to the extent possible given his/her understanding. If the patient is capable of doing so, he/she must indicate assent by personally signing and dating the written informed consent document or a separate assent form. Informed consent must be obtained before conducting any study-specific procedures (e.g. all of the procedures described in the protocol). The process of obtaining informed consent must be documented in the patient source documents.

[figure not shown]
Novartis will provide to Investigators in a separate document a proposed informed consent form that complies with the ICH GCP guideline and regulatory requirements and is considered appropriate for this study. Any changes to the proposed consent form suggested by the Investigator must be agreed to by Novartis before submission to the IRB/IEC, and a copy of the approved version must be provided to the Novartis monitor after IRB/IEC approval.

Women of child bearing potential must be informed that taking the study treatment may involve unknown risks to the fetus if pregnancy were to occur during the study and agree that in order to participate in the study they must adhere to the contraception requirement for the duration of the study and period after discontinuation of study drug. If there is any question that the patient will not reliably comply, they must not be entered in the study.

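### The male condom and no-fathering rules end with active treatment, so men have no stated rule on condoms or unplanned conception from last dose to month 9

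*Protocol*

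**What the plan says.** For men, criterion 7 in Protocol Section 4.2 reads: "Sexually active males, unless they agree to use a condom during active treatment. Male patients should not father a child in this period". The synopsis, under key exclusion criteria, says: "Sexually active males unless they agree to use condom during intercourse while on study drug". It carries no fathering rule.

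Criterion 7 also gives its reason. Vasectomized men must use a condom too, "in order to prevent accidental exposure of their female partner to study drug via seminal fluid". For a planned pregnancy it adds that "the male patient wishing to father a child during the study should discontinue study drug and undergo the accelerated elimination process", citing the long elimination time of teriflunomide.

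Section 7.8 states that, without the accelerated elimination procedure (AEP), "it takes on average 8 months to reach plasma concentrations less than 0.02 mg/L", and that this can take as long as 2 years.

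Section 3.1 covers patients of both sexes who are off drug and have at least 9 months of follow-up. Those "who plan to become pregnant/father a child or do not agree to continue to use highly effective contraception, should undergo the teriflunomide-accelerated elimination procedure".

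For women the post-dose period is written out. Criterion 6 requires contraception for at least 12 months after stopping. Section 10.2 has women of child-bearing potential agree that "they must adhere to the contraception requirement for the duration of the study and period after discontinuation of study drug". Section 10.2 has no counterpart for men.

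**The concern.** The rule stops at the last dose, but the reason given for it does not. If drug in semen justifies a condom on treatment, even after vasectomy, the same reason holds while teriflunomide is still being cleared. Criterion 7 accepts this for planned fathering, where stopping drug is not enough and AEP is added.

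Under the blind, every man off drug has to be handled as possibly exposed to teriflunomide. Section 3.6 lists teratogenicity among its risks, and Section 7.6 collects pregnancy outcomes in female partners of treated men. A site applying criterion 7 as written, with no stricter local rule, has no instruction to give a man who has just stopped drug. Section 4.2 also bars investigators from adding exclusions, so such a site cannot make a post-dose commitment a condition of entry. What is at stake is partner safety, not an estimate or a test.

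**Working it through.** The plan states no figure to reproduce, so the check sets the provisions side by side for a man after his last dose.

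| Provision | What it covers | Covers condom use or unplanned conception before month 9? |
|---|---|---|
| Criterion 7, condom and no-fathering | Active treatment | No |
| Synopsis, condom | While on drug | No |
| Criterion 7, planned fathering | Stop drug and undergo AEP | No, planned fathering only |
| Section 3.1 | AEP from at least 9 months of follow-up | No, though it presumes contraception until then |
| Section 7.8 | AEP after discontinuation, if in the patient's interest or to ease later management | No, discretionary |
| Section 6.5.6, Tables 6-1 and 6-2 | Contraception status checked against protocol requirements, as applicable | No, there is no male post-dose requirement to check against |
| Section 10.2 | Contraception after discontinuation | No, women only |

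The methods that count as highly effective are listed only in criterion 6, the women's criterion. Teriflunomide levels do not fill the gap either: Table 6-2 has them assessed only once a patient has at least 9 months of follow-up.

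Durations, all in months as the protocol gives them:

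- Stated condom period after last dose: men 0, women (contraception) at least 12.
- Window with no stated male rule: last dose to month 9 = 9.
- Average clearance without AEP: 8. Share of the window: 8/9 = 89%.
- Slowest clearance: 2 years = 24. This exceeds the window by 24 − 9 = 15.
- A 12-month rule would exceed average clearance by 12 − 8 = 4 and fall short of the slowest by 24 − 12 = 12.

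A man on teriflunomide with average clearance and no AEP would therefore be above 0.02 mg/L for about 8 of the 9 months in which no condom rule is stated.

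**The case against.** The strongest reply is that the intent is plain and only one sentence is missing. Section 3.1 addresses all patients, names fathering a child, and speaks of continuing contraception, which makes sense only if men were using it up to then. The contraception-status rows in Tables 6-1 and 6-2 are not limited to women, whereas the pregnancy-test footnotes are. Criterion 7 refers to fathering during the study, and the core study includes the Safety Follow-up epoch, so its AEP instruction reaches past the last dose.

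That shows intent, and it fully covers planned fathering. It does not create a requirement. Presuming contraception to month 9 is not the same as asking men for it, and the criterion that does ask says when it ends.

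A second reply is that the answer may lie elsewhere. Section 4.2 makes stricter local requirements binding, Section 7.1 places comparator risks from the local label in the consent, and the consent text is not available here. A stricter rule there cannot be excluded. It would still leave criterion 7 and the synopsis saying something shorter.

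A third reply is that the documents give no seminal concentration and no male-mediated risk. This stands: the partner risk cannot be sized, and 12 months for men is taken from criterion 6, with no male-specific basis.

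**Conclusion.** The point holds in a limited form. From last dose to month 9, no provision in the documents available requires men to use condoms or avoid unplanned conception, although the protocol's own average clearance takes up 8 of those 9 months. It applies to men who stop drug and do not enter the Extension, which has a separate protocol; their number is not given. It assumes that neither the local label nor the consent text is stricter. The change should be made, but no endpoint, power, error rate or analysis is affected.

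Three stronger readings are not supported:

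- **That men may plan to father a child straight after the last dose.** Criterion 7 requires stopping drug and AEP first.
- **That criterion 6 and Section 3.1 contradict each other on AEP timing.** Criterion 6 permits AEP for women after 12 months, while Section 3.1 calls for it once at least 9 months of follow-up are complete. A site can follow both, with AEP at month 9 and contraception continuing to month 12. Aligning the wording would be editorial.
- **That the gap can be counted in days or visits.** The 28-day month in Section 6 belongs to the visit schedule, not to a clearance time. Safety Follow-up visits run from the End of Study visit, not from last dose, so the number of contraception checks inside the window differs between patients.

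**What to change.** Reword criterion 7 and the synopsis along these lines:

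> Excluded: sexually active men who do not agree to use condoms, and not to father a child, throughout treatment and for 12 months after the last dose; this commitment ends earlier if the accelerated elimination procedure (Section 7.8) has been completed.

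Keep the existing criterion 7 text on vasectomized men and planned fathering. Add a matching sentence for men to Section 10.2.

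Apply the rule in both arms, with no early release on an individual teriflunomide level. Section 3.1 tells sites only whether follow-up must continue, and that also depends on B-cell repletion, so a release tied to drug level alone could reveal the arm. Release on AEP keeps the blind, because under Section 3.1 "the decision to do the accelerated elimination procedure must be made without knowledge of the core study treatment assignment".

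The cost is an amendment, consent wording, and a longer condom commitment for men in both arms, including those who never received teriflunomide. Two limits remain. Twelve months does not cover the slowest eliminators; for them the Section 3.1 AEP rule continues to apply. Release on completing AEP is not confirmed by a plasma level, which is the price of protecting the blind. No new visits, samples or analyses are needed.

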5.1 Study treatment

5.1.1 Investigational and control drugs

Investigational drug will be provided in pre-filled syringes for subcutaneous administration containing 20 mg ofatumumab (50 mg/ml, 0.4 ml content). Ofatumumab (OMB157) is clear to opalescent, colorless to pale yellow, essentially particle-free liquid in a pre-filled syringe. The matching placebo to ofatumumab pre-filled syringe will have the same appearance as the investigational drug.

Control treatment, teriflunomide (Aubagio®) 14 mg, will be provided as over-encapsulated tablets (either a hard gelatin capsule or a hydroxy propyl methyl cellulose (vegetarian-based) capsule will be used, referred to as capsule hereafter) for oral administration. Teriflunomide-matching placebo capsule (capsule containing placebo-tablet) will have the same appearance as the active comparator. Teriflunomide and teriflunomide-matching placebo capsules will be provided in blisters. It is possible that a switch from blisters to bottles will be performed during the course of the study.

Study drug will be supplied by Novartis.

5.1.2 Additional treatment

No additional treatment beyond investigational drug and comparator drug are provided as part of study drug supplies for this study.

5.2 Treatment arms

The study includes 2 treatment arms:

- Ofatumumab arm: ofatumumab 20 mg sc injections on Day 1, 7, 14, Week 4 (Study Month 1) and every 4 weeks thereafter + teriflunomide-matching placebo capsule orally once daily.
- Teriflunomide arm: teriflunomide 14 mg capsule orally once daily + ofatumumab-matching placebo injections on Day 1, 7, 14, Week 4 (Study Month 1) and every 4 weeks thereafter.

5.3 Treatment assignment and randomization

Eligible patients will be randomized in a 1:1 ratio to either the active ofatumumab 20 mg group or to the active teriflunomide 14 mg group. The randomization will be stratified by geographical region and by MS subtype (RRMS, SPMS). Study sites can only participate in one of the 2 studies to ensure independence of each study.

On Day 1 (randomization visit), all eligible patients will be randomized via Interactive Response Technology (IRT) to one of the treatment arms. The Investigator or his/her delegate will contact the IRT after confirming that the patient fulfills all the inclusion/exclusion criteria. The IRT will assign a randomization number to the patient, which will be used to link the patient to a treatment arm and will specify a unique medication number for the first package of investigational treatment to be dispensed to the patient. The randomization number will not be communicated to the caller.

The randomization numbers will be generated using the following procedure to ensure that treatment assignment is unbiased and concealed from patients and Investigator staff. A patient randomization list will be produced by the IRT provider using a validated system that automates the random assignment of patient numbers to randomization numbers. These randomization numbers are linked to the different treatment arms, which in turn are linked to medication numbers. A separate medication list will be produced by or under the responsibility of Novartis Drug Supply Management using a validated system that automates the random assignment of medication numbers to packs containing the investigational drug(s).

